### **5.5 Withdrawal Criteria (if applicable)**

If at any time during the study the investigator determines that a subject's safety has been compromised, the subject may be withdrawn from the study.

Subjects may withdraw consent from the study at any time.

Sponsor and/or investigator may discontinue any subject for non-compliance or any valid medical reason (see [Section 8.6.2](#)).

## **6 STUDY PARAMETERS**

### **6.1 Efficacy Measures**

#### **6.1.1 Exploratory Pharmacodynamic Variables**

The following exploratory endpoints will be tested:

- [REDACTED]
- Ora CalibraTM Ocular Discomfort Scale;

## 6.2 Safety Measures

- Visual acuity (ETDRS);
- Slit-lamp biomicroscopy;
- Adverse event query;
- Undilated Fundoscopy;
- Intraocular Pressure;

# 7 STUDY MATERIALS

## 7.1 Study Drug(s)

### 7.1.1 Formulations

#### Randomized Study Treatments

- ADX-102 Ophthalmic Solution (0.5%)
- ADX-102 Ophthalmic Solution (0.1%)
- ADX-102 Ophthalmic Lipid Solution (0.5%)

### 7.1.2 Dispensation Schedule

- At the end of Visit 1, qualified subjects will be randomized and the first dose of study drug will be administered in office. A supply of ADX-102 Ophthalmic Solution (0.5%), ADX-102 Ophthalmic Solution (0.1%), or ADX-102 Ophthalmic Lipid Solution (0.5%) will be dispensed for dosing QID.
- At the end of Visit 2, the unused vials from their Visit 1 kit will be re-dispensed to subjects, and a second kit for dosing through Visit 3 will also be dispensed.
- At Visits 2 and 3, remaining/used study drug will be collected from subjects for drug accountability.
- Subjects will be instructed to not use study drug on the day of visits (Visit 2 and 3) prior to the visit.

### 7.1.3 Instructions for Use

Subjects will be instructed to dose in each eye QID (morning, noon, afternoon, and in the evening before bed). A horizontal line of text has been completely blacked out with a solid black rectangle.

A large rectangular area of the page has been completely blacked out with a solid black rectangle, obscuring several lines of text.

## 7.2 Other Study Supplies

Other study supplies include urine pregnancy tests, [REDACTED]  
[REDACTED]  
[REDACTED]

# 8 STUDY METHODS AND PROCEDURES

## 8.1 Subject Entry Procedures

### 8.1.1 Overview

Subjects, as defined by the criteria in [Sections 5.2, 5.3, and 5.4](#), will be considered for entry into this study.

### 8.1.2 Informed Consent

Prior to a subject's participation in the trial (i.e., prior to changes in a subject's medical treatment and/or prior to study related procedures), the study will be discussed with each subject, and subjects wishing to participate must give written informed consent using an informed consent form (ICF). The ICF must be the most recent version that has received approval/favorable review by a properly constituted Institutional Review Board (IRB).

### 8.1.3 Washout Intervals

Prohibited medications, treatments, and activities are outlined in the exclusion criteria (Section 5.4).

### 8.1.4 Procedures for Final Study Entry

Subjects must meet all inclusion and none of the exclusion criteria.

### 8.1.5 Methods for Assignment to Treatment Groups

Prior to initiation of study drug (at Visit 1), each subject who qualifies for entry will be assigned a screening number. All screening numbers will be assigned in strict numerical sequence at a site and no numbers will be skipped or omitted. If all inclusion and exclusion criteria are met at Visit 1, each qualifying subject will then be assigned a randomization number at the end of Visit 1.

A randomization schedule will be provided to the investigational site. The randomization schedule will use block randomization, such that there will be an approximate equal number of subjects assigned to each of the three treatment arms at the site. The site staff will dispense to the patient the study kit labeled with the corresponding randomization number. The randomization number will be recorded on the patient's source document and electronic case report form (eCRF). A new kit will be dispensed at Visit 2 based on the subject's randomization. The Sponsor, Investigators,

and study staff will be masked during the randomization process and throughout the study.

## 8.2 Concurrent Therapies

The use of any concurrent medication, prescription or over-the-counter, is to be recorded on the subject's source document and corresponding eCRF along with the reason the medication was taken.

Concurrent enrollment in another investigational drug or device study is not permitted.

### 8.2.1 Prohibited Medications/Treatments

Disallowered medications/treatments during the study are outlined in the Exclusion Criteria ([Section 5.4](#)).

### 8.2.2 Escape Medications

No escape medications are required for this study.

### 8.2.3 Special Diet or Activities

No special diets or activities are required for this study.

## 8.3 Examination Procedures

### 8.3.1 Procedures to be Performed at Each Study Visit with Regard to Study Objective(s)

The following procedures will be performed (see [Appendix 2](#) for description):

#### **Visit 1 (Day 1): Screening & Enrollment**

- Informed consent / HIPAA;
- Demographic data and medical / medication history;
- Review of qualification criteria;
- Urine pregnancy test (for females of childbearing potential);
- Ora Calibra® Ocular Discomfort;
- [REDACTED]
- [REDACTED]
- [REDACTED]
- Visual Acuity (ETDRS);
- Slit-lamp Biomicroscopy;
- [REDACTED]
- [REDACTED]
- At least 20-minute wait;
- [REDACTED]

- Fluorescein staining – Ora Calibra®;
- Lissamine Green staining – Ora Calibra®;
- [REDACTED]
- [REDACTED]
- Intraocular Pressure;
- Undilated Fundoscopy;
- Adverse event query;
- Review of qualification criteria;
- Randomization & Dispensation of study drug kit according to randomization for QID dosing until Visit 2;
- [REDACTED]
- [REDACTED]
- Subjects will be instructed to dose in each eye four times daily (morning, noon, afternoon, and in the evening before bed);
  - Subjects will be instructed to dose in each eye before bed in the evening of Visit 2;
  - Subjects will be instructed to not dose with study drug on the morning of their next visit (Visit 2);
- Qualified subjects will be scheduled for Visit 2.

#### Visit 2 (Day 8 ± 1): 1-Week Follow-Up

- Collection and review of study drug;
- Subject will be asked if he/she dosed with study drug on the morning of the visit; if the subject indicates he/she dosed that morning, he/she should wait at least 4 hours from the time of dosing before efficacy assessments are performed;
- Medical/medication history update;
- Adverse event query;
- Ora Calibra® Ocular Discomfort;
- [REDACTED]
- [REDACTED]
- [REDACTED]
- Visual Acuity (ETDRS);
- Slit-lamp Biomicroscopy;
- [REDACTED]
- [REDACTED]
- Dispensation of study drug kits for QID dosing until Visit 3;
- [REDACTED]
- [REDACTED]

- Subjects will be instructed to dose in each eye four times daily (morning, noon, afternoon, and in the evening before bed);
  - Subjects will be instructed to dose in each eye before bed the evening of Visit 3;
  - Subjects will be instructed to not dose with study drug on the morning of their next visit (Visit 3);
- Subjects will be scheduled for Visit 3.

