### Visit 3 (Day 29 ± 2): 4-Week Follow-Up and Study Exit

- Collection and review of study drug;
- Subject will be asked if he/she dosed with study drug on the morning of the visit; if the subject indicates he/she dosed that morning, he/she should wait at least 4 hours from the time of dosing before efficacy assessments are performed;
- Medical/medication history update;
- Adverse event query;
- Urine pregnancy test (for females of childbearing potential);
- Ora Calibra® Ocular Discomfort;
- [REDACTED]
- [REDACTED]
- [REDACTED]
- Visual Acuity (ETDRS);
- [REDACTED]
- Intraocular Pressure;
- Undilated Fundoscopy;
- Adverse event query;
- Study Exit.

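### The pre-assessment dosing check at Visits 2 and 3 asks only about a morning dose, so a noon or afternoon drop before a later visit can escape the 4-hour wait

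*Protocol*

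**What the plan says.** Four parts of the protocol bear on dosing before a follow-up visit.

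- **The general rule, 7.1.2 (Dispensation Schedule):** "Subjects will be instructed to not use study drug on the day of visits (Visit 2 and 3) prior to the visit". It covers every dose slot before the visit.
- **The regimen, 7.1.3 (Instructions for Use):** "Subjects will be instructed to dose in each eye QID (morning, noon, afternoon, and in the evening before bed". That makes four slots a day.
- **The instructions given at the preceding visit, 8.3.1:** at Visit 1, "Subjects will be instructed to not dose with study drug on the morning of their next visit (Visit 2") and "Subjects will be instructed to dose in each eye before bed in the evening of Visit 2"; at Visit 2, "Subjects will be instructed to not dose with study drug on the morning of their next visit (Visit 3") and "Subjects will be instructed to dose in each eye before bed the evening of Visit 3". Neither pair mentions the noon or afternoon dose of the visit day.
- **The site check, 8.3.1, worded identically at Visits 2 and 3:** "Subject will be asked if he/she dosed with study drug on the morning of the visit; if the subject indicates he/she dosed that morning", then "he/she should wait at least 4 hours from the time of dosing before efficacy assessments are performed".

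Visit windows are given in days only (Day 8 ± 1, Day 29 ± 2). SAP 14.6 compares the arms on the Ocular Discomfort Scale at each visit, both as observed means and as changes from baseline.

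**The concern.** The 4-hour wait shows that the protocol does not want efficacy assessed soon after a drop. The site question is there because some subjects will dose despite being told not to. A back-up check should cover the same breaches as the rule it supports, and this one does not: the rule covers the whole pre-visit day, while the check covers the morning.

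The gap opens when a visit falls at midday or later and the subject has taken a noon or afternoon drop beforehand, either in breach of 7.1.2 or because only the 8.3.1 wording was passed on. That subject answers the question correctly, no wait is triggered, and the discomfort rating follows after only a history update and an adverse event query. The rating may then reflect the recent drop as well as the course of treatment. The documents do not give the direction or size of such an effect. Nor do they show that it would be the same for the two concentrations and the lipid formulation.

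**Working it through.** The plan states no figure on this point, so the check sets the passages side by side and counts what they cover.

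**Coverage by slot, visit day, before the visit**

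| Slot (7.1.3) | Barred by 7.1.2 | Barred by name in the 8.3.1 instruction | Asked about in the 8.3.1 check |
|---|---|---|---|
| Morning | yes | yes | yes |
| Noon | yes, if before the visit | no | no |
| Afternoon | yes, if before the visit | no | no |

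The fourth slot, before bed, is taken not to precede a same-day visit. Slots that could precede the visit: 4 − 1 = 3. Named by the check: 1. Not named: 3 − 1 = 2. The two unnamed slots matter only if visits are late enough for those doses to come first.

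**Is there a conflict between 7.1.2 and 8.3.1?** Not strictly. Nothing in 8.3.1 expressly permits a noon drop before the visit, and a subject who takes no drug before the visit obeys both sections. The mismatch is one of scope.

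**When a noon dose falls inside the wait.** The documents give no clock times, so these are assumptions. The 4-hour interval ends at:

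- dose at 11:30: 11:30 + 4 h = 15:30
- dose at 12:00: 12:00 + 4 h = 16:00
- dose at 13:00: 13:00 + 4 h = 17:00

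An efficacy assessment before that time is too early by the protocol's own standard. Take a 14:00 assessment as an example. A dose at 08:00 is 6 hours old and already satisfies the wait; a dose at 12:00 is 2 hours old and does not. The check asks about the first and not the second.

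**Ratings under the check.** 45 planned subjects x 2 post-baseline visits = 90 discomfort ratings, assuming no dropout. This is the number the check governs, not the number affected. With 15 subjects per arm, one subject contributes 1/15 = 6.7% of an arm mean. Because SAP 14.6 analyses the ITT population with LOCF, a Visit 2 rating can also stand in for a missing Visit 3 rating.

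**What cannot be computed.** The number of subjects affected, the effect of one drop on the rating and the standard deviation are not in the documents, so no shift in an arm mean is estimated.

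**Comparison with baseline.** Exclusion criterion 4 bars any eye drops in the 2 hours before Visit 1, whatever the time of day. The protocol therefore already uses a rule based on elapsed time at baseline; the follow-up check is tied to a slot instead.

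**The case against.** The main control is in place. Section 7.1.2 bars every pre-visit dose, so a subject who follows it never reaches the gap. What remains needs several things together: a visit at midday or later, a drop taken beforehand, a literal answer to the question, and staff who do not notice it when they collect and review study drug at the start of the visit. Section 8.5 also provides written instructions. No readable text shows that this combination will occur. All of this stands, and it keeps the severity low. It does not repair the check, whose purpose is to catch subjects who departed from the rule. No readable text links the vial review to the time of the last dose or to the wait.

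A second argument is that the drafters had morning visits in mind. Study drug is collected at Visit 3 and none is listed as dispensed, so the line about dosing on the evening of Visit 3 does not work literally and may mean the evening before. Read that way, the sequence is to dose the night before, skip the morning and attend. This is plausible. If all visits are in the morning the gap is zero, but the readable text does not say so.

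Third, text is blacked out in 7.1.3, in 8.3.1 just before the dosing instructions, in 8.5, in 11.5.3, in Appendix 2 and in SAP 12.1, and any of these could hold a further control. That limits confidence in how the whole procedure works. The sentence containing the check is readable in full and names only the morning.

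Finally, there are no primary or secondary endpoints and no formal hypotheses. All three arms follow the same rule under masked block randomization, so there is no stated reason to expect bias towards one arm. That also stands. The slot count and the 90 ratings describe the reach of the check and are not an effect size.

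**Conclusion.** The point holds as a low-severity improvement. As worded, the check at Visits 2 and 3 cannot detect a noon or afternoon dose taken before a later visit, although 7.1.2 forbids such a dose and the 4-hour wait is meant to keep recent dosing away from efficacy assessments. How often this would happen is unknown and may be never; the effect on any arm comparison is also unknown. The conclusion rests on three assumptions: that some visits may take place at midday or later, that some subjects may dose before them, and that the blacked-out text contains no broader check. Confidence is medium for that reason.

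**What to change.** Make two wording changes in 8.3.1.

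1. At Visits 2 and 3, replace the morning question with: *Has any study drug been used today before this visit, and at what time was the most recent dose?* Run the existing 4-hour wait from that dose.
2. In the instructions given at Visits 1 and 2 for the next visit, replace the morning restriction with the scope of 7.1.2: no study drug on the visit day until the visit is over. While editing, clarify which evening the before-bed line refers to.

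The cost is small. The wait already runs from a dosing time, so at most one data field is added. A few subjects may wait longer at the site. The design, sample size and analysis do not change.

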## SYNOPSIS

Protocol Title:	A Single-Center, Phase 2a, Randomized, Double-Masked, Clinical Study to Assess the Safety, Tolerability, and Pharmacodynamic Activity of ADX-102 Ophthalmic Solution in Subjects with Dry Eye Syndrome
Protocol Number:	ADX-102-DES-007
Study Drug:	1) ADX-102 Ophthalmic Solution (0.5%) 2) ADX-102 Ophthalmic Solution (0.1%) 3) ADX-102 Ophthalmic Lipid Solution (0.5%)
Study Phase:	2a
Study Objective:	The objective of this study is to evaluate the safety, tolerability, and pharmacodynamic activity of ADX-102 Ophthalmic Solutions and ADX-102 Ophthalmic Lipid Solution in subjects with dry eye syndrome.
Overall Study Design	
Structure:	Single-center, double-masked, randomized study
Duration:	An individual subject's participation is estimated to be approximately 4 weeks (28 days).
Dosage/Dose Regimen:	Subjects eligible to be randomized will receive one of the following treatments to be administered bilaterally four times daily (QID) for 28 days (from Visit 1 to Visit 3). 1) ADX-102 Ophthalmic Solution (0.5%) 2) ADX-102 Ophthalmic Solution (0.1%) 3) ADX-102 Ophthalmic Lipid Solution (0.5%)
Summary of Visit Schedule:	3 visits over the course of approximately 4 weeks 

• Visit 1 = Day 1, Screening and Enrollment

• Visit 2 = Day 8 ± 1, 1-Week Follow-Up

• Visit 3 = Day 29 ± 2, 4-Week Follow-Up

Measures Taken to Reduce Bias:	This is a randomized treatment assignment, double-masked study.
Study Population Characteristics	
Number of Subjects:	Approximately 60 subjects will be screened to enroll 45 subjects (15 per treatment arm).
Condition/Disease:	Dry Eye Syndrome (DES)

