15.1 Adverse Events

An AE is defined as any untoward medical occurrence associated with the use of a drug in humans, whether or not the event is considered drug-related. An AE can therefore be any unfavorable and unintended sign (e.g., an abnormal laboratory finding), symptom, or disease occurring after the subject started dosing with the study drug, without any judgment about causality. Any pre-existing medical condition that worsens after administration of the study drug will also be considered a new adverse event. The AE reporting period ends upon study exit. Study drug includes the investigational drug under evaluation. All AEs will be coded using MedDRA Version 20.0.

Treatment-emergent adverse events (TEAEs) are defined as any adverse event that occurs or worsens after the first dose of study treatment. AEs recorded in the eCRF which began prior to treatment will not be included in the summary tables but will be included in the AE data listings.

An overall summary will be presented that includes the number of AEs, TEAEs, serious AEs (SAE), and serious TEAEs (TE-SAE). The summary will also include the number and percentage of subjects withdrawn due to an AE, the number and percentage of subjects with an AE resulting in death, and the number and percentage of subjects who experienced at least one AE, TEAE, SAE and TE-SAE, by treatment group and for all subjects. This summary will include breakdowns of AEs further categorized as ocular or non-ocular.

Additional summaries of TEAEs will be provided showing the number and percentage of subjects who experienced at least one TEAE. These summaries will be presented by SOC and PT. Non-ocular TEAEs will be summarized using discrete summary statistics and presented by treatment group at the subject and event level by SOC and PT. Ocular TEAEs will be similarly summarized at the subject and event level as well as for study and fellow eyes separately. If a subject reports the same PT multiple times within the same SOC, that PT will only be reported once within that SOC. As with the PT, if a subject reports multiple conditions within the same SOC, that SOC will only be reported once. In the summary, SOC will be listed in order of descending frequency for all subjects; PTs will be listed in order of descending frequency for all subjects within each SOC. The occurrence of non-ocular and ocular TEAEs will also be tabulated by SOC, PT, and maximal severity.

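### Does the instruction to dose on the evening of Visit 3, after drug return and study exit, disturb exposure, adverse-event capture or the timing of assessments?

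*Protocol*

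**What the plan says.** Protocol Section 8.3.1 lists what subjects are told at each visit. At Visit 2 the list includes "Subjects will be instructed to dose in each eye before bed the evening of Visit 3", followed by an instruction not to dose on the morning of Visit 3. The Visit 1 list has the same pair for the next visit: "Subjects will be instructed to dose in each eye before bed in the evening of Visit 2", then no dosing that morning.

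Other text bears on when dosing ends:

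- The Synopsis describes treatment as "administered bilaterally four times daily (QID) for 28 days (from Visit 1 to Visit 3".
- The Visit 2 list itself has "Dispensation of study drug kits for QID dosing until Visit 3".
- Protocol Section 7.1.2 is a little looser: "a second kit for dosing through Visit 3 will also be dispensed". It also says "At Visits 2 and 3, remaining/used study drug will be collected from subjects for drug accountability", and describes re-dispensing of unused vials at Visit 2 only.
- The Visit 3 list opens with "Collection and review of study drug" and closes with study exit. Protocol Section 8.5 likewise has used and unused vials collected up to and including Visit 3.
- The schedule in SAP Section 3.2 marks dispensation and self-instillation at Visits 1 and 2, with no mark at Visit 3.
- SAP Section 15.1 states "The AE reporting period ends upon study exit".
- SAP Section 12.2 computes exposure for completed subjects as the completion date minus the Visit 1 date.

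**The concern.** Read literally, every subject is told to take a dose on an evening when the protocol has left them no drug and they have already exited. A subject who kept vials back in order to comply would take one bilateral dose after drug accountability, after the last adverse-event query and after the reporting period has closed. Protocol Section 9.5 follows unresolved events and new information on existing serious events; it does not collect new events after exit. The exposure formula would also miss that day.

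There is a second worry. Each evening line is paired with a no-morning-dose line for the same visit, which suggests that the pair was meant to fix the interval between the last dose and the ocular discomfort and other assessments. As worded, the evening line concerns a time after those assessments. If nothing else set the interval, it could vary between subjects and add noise to the exploratory comparisons.

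**Working it through.** **Inputs.** Day 1 is the day of randomization and there is no Day 0 (SAP Section 3.1). The first dose is given in the office at Visit 1 (Protocol Section 7.1.2). Visit 3 is Day 29 ± 2. The Synopsis states 28 days of dosing.

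**The plan's own figure.** Exposure for a completer = Visit 3 day - 1. At the nominal visit, 29 - 1 = 28 days. This reproduces the Synopsis figure, and it equals the count of calendar dosing days when none falls on the day of Visit 3 (Days 1 to 28).

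**Adding a dose on the evening of Visit 3.** Calendar dosing days = Visit 3 day.

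| Visit 3 on day | SAP completer exposure | Dosing days, none on Visit 3 day | Dosing days with a Visit 3 evening dose |
|---|---|---|---|
| 27 | 26 | 26 | 27 |
| 28 | 27 | 27 | 28 |
| 29 | 28 | 28 | 29 |
| 30 | 29 | 29 | 30 |
| 31 | 30 | 30 | 31 |

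The gap is one day across the whole window, and it exists only in the last column. Without the extra dose, the formula and the Synopsis agree. (The separate formula for subjects lost to follow-up adds one day. That is a different matter and does not concern completers.)

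**Can the extra dose happen?** Drug is collected as the first step of Visit 3, both used and unused vials are covered, re-dispensing is described for Visit 2 only, and the SAP schedule shows none at Visit 3. If these steps are carried out, the number of subjects able to dose that evening is zero. The upper bound, if every subject kept vials back, is one bilateral dose in each of approximately 45 subjects.

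**Does adverse-event reporting conflict?** The end of reporting at exit contradicts nothing unless a dose follows exit. It stands or falls with the previous step.

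**Is the Visit 1 line also impossible?** No. At Visit 2, unused vials are returned to the subject and a second kit is added, so an evening dose that day can be taken. Skipping that morning's dose is compatible with it.

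**Is the interval from last dose to assessment left open?** Three rules that do not depend on the disputed line bear on it: four daily doses, one of them before bed (Protocol Section 7.1.3); no study drug before the visit on the days of Visits 2 and 3 (Section 7.1.2); and a wait of at least 4 hours before efficacy assessments if a subject did dose that morning (Section 8.3.1). Together they identify the last scheduled dose before each assessment and set a minimum interval for those who depart from it. The remaining variation comes from bedtime, clinic time and non-compliance. All three arms receive the same instructions under masking, so there is no evident route to a difference between arms.

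**The case for a change.** The best case for acting is that this is an instruction spoken to every subject, that it contradicts several other places in the protocol, and that the remedy is cheap: one clarified bullet and a consistent instruction sheet, with no added visits or data. A conscientious subject might hold back a vial, and any reaction to that dose would go unrecorded. Redaction does not explain the conflict away, because the instruction, the collection step, the exit step, the schedule rows and the reporting-period sentence are all legible.

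Most of this stands as a point about wording. The passages do disagree and must be reconciled. What does not stand is the step from there to the analysis. The unrecorded dose requires that drug return fail, although the protocol states that return in three places. The exposure and adverse-event conflicts are consequences of assuming that dose, not separate faults in SAP Sections 12.2 and 15.1.

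Redaction also limits how far the argument about intervals can go. Most of Protocol Section 7.1.3, some bullets beside the dosing instructions in Section 8.3.1 and the dosing-compliance text in SAP Section 12.1 are blacked out, so more on the last dosing occasion may be stated there.

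**Conclusion.** A clerical slip in one bullet of the Visit 2 list. It should be brought into line with Protocol Section 7.1.2, the Visit 3 steps and the Synopsis whenever that text is next handled. This review takes no view on which dosing occasion is the intended last one. No change to the design or the statistical plan follows.

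The size of the effect as the plan operates is nil: completer exposure stays at 28 days nominal (26 to 30 over the visit window), the safety summaries cover the same period as the dosing, and the comparisons of ocular discomfort are untouched. If drug return failed, the effect would be at most one uncounted dosing day and one unmonitored bilateral dose per affected subject. The study has no primary endpoint and no formal hypotheses, so no confirmatory conclusion rests on the point either way.

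This rests on two assumptions: that drug is collected at Visit 3 as described, and that the blacked-out instructions do not arrange a further supply at exit. The visible SAP schedule, with no dispensation at Visit 3, supports the second.
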